5.4 Pharmacokinetic Evaluation

Each infant participating in the phase 1 trial will undergo blood sampling on day 7 to measure serum tobramycin peak and trough levels. Up to 6 random blood samples (200µL per sample) will also be collected concurrent with clinical blood draws. Based on prior studies, we anticipate that most trial participants, particularly those receiving the lowest dosages of inhaled tobramycin, will have serum trough levels below the lower limit of quantification in the clinical lab (0.6µg/mL).^{21,48,90} Therefore, we will collect 200µL of blood for high resolution measurement of peak, trough and random plasma tobramycin levels as per section 6.3.4. Blood samples collected for PK analyses will be stored at -80c in vials labelled with a study ID number only. Sample batches will be shipped to and subsequently processed at the University of Florida College of Pharmacy. This laboratory has extensive experience with high-resolution drug level testing and has established assays for tobramycin.

6 STATISTICAL CONSIDERATIONS

6.1 **Primary Endpoint**

The primary study endpoint is a composite safety endpoint. The presence of any of the following events occurring at any timepoint during the 14-day phase 1 trial will define a toxic drug response:

- Trough serum tobramycin level (measured 11 hours after the last administered dose) ≥1µg/mL
- Increase in serum creatinine level by ≥0.3mg/dL above the pre-trial level
- Increase in serum creatinine >1.5-fold above the pre-trial level
- Urine output <0.5mL/kg/hr for 12 hours
- Any serious adverse event possibly attributable to the investigational drug

6.2 Secondary Endpoints

Additional exploratory secondary safety endpoints are:

 New onset or worsened coughing associated with a change in respiratory status (SpO₂ <80% for >10 seconds; need for increase in FiO₂ by >20%)

- Obstruction of the endotracheal tube requiring tube replacement
- Unplanned tracheal extubation
- Desaturation (SpO₂ <80% for >10 seconds) during administration of inhaled tobramycin
- Rates of pre-discharge failed audiology examinations
- Rates of new intra-patient microbial resistance to tobramycin
 - Bacterial antimicrobial sensitivities reported for the pre-treatment tracheal aspirate culture will be compared to the tracheal aspirate cultures collected during and post treatment. The presence of new-onset microbial resistance to tobramycin within a patient – a change from susceptible to resistant by the same organism – will be recorded

The exploratory secondary efficacy endpoints are:

- Tracheal aspirate tobramycin levels
- Change in tracheal aspirate pathogenic bacterial colony forming unit (CFU) counts measured by high resolution, quantitative culture
- Longitudinal change in the following measures of administered respiratory support: FiO₂, ventilator mean airway pressure (MAP), respiratory severity score (MAP x FiO₂)
- Change in the following measures of hypoxemia (SpO₂<80%): intermittent hypoxemia (events lasting 10s-3min), prolonged hypoxemia (events lasting >1min), and daily proportion of time with hypoxemia
- Change in tracheal aspirate cytokine levels, neutrophil/WBC ratio, and patterns in the airway microbiome
- Longitudinal change in dynamic compliance, peak expiratory flow, airway resistance, and carbon dioxide elimination

6.3 Statistical Methods

6.3.1 Baseline Data

Baseline and demographic characteristics will be summarized using standard descriptive statistics (e.g., means and standard deviations for continuous variables such as age and percentages for categorical variables such as gender).

6.3.2 Safety Analysis

All subjects entered into the phase 1 investigational drug trial of inhaled tobramycin will be included in the safety analysis. The primary study outcome is a safety endpoint and will be evaluated as a dichotomous outcome based on the presence of any of the events listed in section 6.1. The 3+3 design flow diagram shown in **Figure 8** will be followed to determine enrollment and trial progression based on the results of each infant's safety analysis. In addition, the frequencies of AEs by type, body system, severity, and relationship to the study drug will be summarized. SAEs (if any) will be described in detail.

6.3.3 Exploratory Secondary Safety and Efficacy Analyses

The exploratory secondary safety and efficacy endpoints listed in section 6.2 will be analyzed as described in **Table 7** (next page). In brief, all study data will first be summarized using standard descriptive statistics as appropriate based on data type and distribution. Assessments of change over time for all longitudinal secondary outcome data will first be assessed graphically, with and without stratification by the administered tobramycin dose. Next, paired t-tests or Wilcoxon sign rank tests will be used to compare

pre-trial baseline values to those recorded at later time points. Non-paired tests will be used to compare data baseline and subsequent data points between the infants in the phase 1 trial and observational (non-treated) cohorts.

	Values available for:			
Study outcome	Phase 1 trial cohort	Observational cohort	Statistical approach	
Secondary safety endpoints	Yes	Yes, for some endpoints	 Rates of the secondary tolerability endpoints will be summarized for each dose level. Descriptive, narrative details of these endpoints will also be provided as appropriate. Data on the rates of endotracheal tube obstruction, unplanned tracheal extubation, and audiology testing results will be compared between the trial and observational cohorts. Planned comparisons of audiology testing results are described in the Protection of Human Subjects document. 	
Secondary efficacy endpoints				
Negative TA culture for the target GNR	Yes	No	 Primary exploratory efficacy endpoint. Rates will be summarized for the trial cohort as a whole and stratified by drug dose level. 	
Change in TA GNR pathogen CFU	Yes	No	 Absolute (pre vs post) and relative change ([post trial – pre trial] / pre trial) in the target organism CFU/mL on the log₁₀ scale will be calculated for each phase 1 trial participant. Paired t-tests or Wilcoxon sign rank tests as appropriate will be used to compare pre- vs. post-trial absolute CFU/mL values for the whole cohort and stratified by drug dose level. 	
Tracheal aspirate tobramycin levels	Yes	No	 Values, stratified by drug dose, will be compared to established concentrations necessary to overcome the minimum inhibitory concentration needed to kill 90% of detected bacterial isolates (MIC₉₀).^{90,91} Values will also be used in our PK analyses. 	
Tracheal aspirate cytokine levels	Yes	No	 Individual cytokine levels measured pre-trial, ≤48 hours after the final dose, and 14 days after the final drug dose will be summarized. Transformation (e.g. logarithmic) or categorization by centiles will be considered based on the data distribution. Correction for total protein levels in the tracheal aspirate will be employed to account for differences in dilution during sample collection. The relative intra-patient change for the individual cytokine levels 	
			 from pre-trial baseline to the 2 post-trial timepoints will be calculated and compared between dose levels. The association between change in cytokine levels and tobramycin dose will be explored using bivariate and multivariate correlation analyses with Bonferroni correction for multiple testing.¹⁰⁰ We will consider exploratory cluster and linear discriminate analyses to identify airway immunological profiles associated with differences in the response to inhaled tobramycin (e.g. change in CFU/mL).^{101,102} 	
Respiratory support measures Hypoxemia (SpO ₂ <80%)	Yes	Yes	 Continuously recorded FiO₂, MAP, and RSS values will be converted to time-weighted daily averages for each study day. Continuously recorded SpO₂ data will be used to calculate daily rates of intermittent and prolonged hypoxemia and daily total hypoxemia exposure. Assessment of longitudinal change using linear mixed effects models will be considered. 	
Pulmonary mechanics	Yes	Yes	 Infants in both study cohorts will undergo pulmonary mechanics measurements pre-trial, after 7d, and after 14d. Intra-patient change, relative to pre-trial baseline, will be calculated for each participant and compared (1) between the two cohorts and (2) stratified by drug dose. Assessment of longitudinal change using linear mixed effects models will be considered. 	

Table 7. Planned statistical techniques and data availability for the phase 1 trial outcomes

CFU, colony forming units; GNR, Gram-negative rod; TA, tracheal aspirate

We will *consider* constructing exploratory linear mixed effects models to evaluate the longitudinal change in repeated measures outcome data. Owing to the modest total study sample size and low numbers of infants treated with each tobramycin dose, these analyses will only be performed on an exploratory basis if graphical evaluations of the study data suggest strong evidence of a linear change over the course of the study period. These models will be considered: (1) for the phase 1 trial participants as a whole, (2) with stratification by the administered dose of inhaled tobramycin, and (3) between infants who participate in the phase 1 trial and those enrolled in the observational (non-treated) cohort (for the study outcome data collected in both cohorts). Treatment dose group and treatment week will be included in the models as independent variables (the latter is added to account for natural fluctuation in disease acuity over time). Random effects for intercept +/- slope will be considered based on their effect on model fit assessed using the Akaike information criterion. Backwards, stepwise elimination techniques to determine inclusion of possible confounding, independent covariates will be employed to account for measured differences between comparison groups. Adherence to accepted numbers of independent covariates based on the study sample size will be used to avoid model over-fitting.⁹⁸ If longitudinal models are performed, 95% confidence intervals for all estimates of effect will be reported and caution will be urged when interpreting these hypothesis generating results.

Patterns in the airway microbiome will be assessed by comparing (pre vs. post treatment) measures of alpha diversity (e.g. species counts, Shannon index) and beta-diversity (Weighted and unweighted UniFrac distances⁹⁹). Principal coordinate analyses and evaluation of dominant taxa will also be used to compare the microbiome before versus after completing treatment and with stratification by the administered dose of inhaled tobramycin. Linear mixed effects models, appropriate for repeated measures data, will also be constructed to measure the association between the dose of inhaled tobramycin and measures of alpha diversity.

Lastly, hypothesis generating analyses will assess changes in bacterial CFU/mL (on the log₁₀ scale) as a function of: (1) the GNR organism cultured from the tracheal aspirate, (2) pre-trial airway cytokine levels, (3) pre-trial RSS, and (4) pre-trial pulmonary mechanics measurements. These data will help inform the selection of pre-specified subgroups group analyses that will be performed in future randomized trials.

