	• To determine the maximum, safely tolerated dose of tobramycin solution for inhalation (selected between 78mg, 150mg, 216mg, and 300mg administered every 12 hours) in very preterm infants with BPD who are actively receiving invasive mechanical ventilation and have evidence of a pathogenic GNR bacteria (listed in section 3.4.3) detected by tracheal aspirate culture.
	Secondary
	 To evaluate the association between the dose of inhaled tobramycin, plasma tobramycin pharmacokinetics, and peak tracheal aspirate tobramycin levels.
	• To compare the change (pre vs. post study) in tracheal aspirate pathogenic bacterial colony forming unit (CFU) counts measured by high resolution culture, (1) between participants in the phase 1 trial and untreated infants in the observational cohort, and (2) between trial participants stratified by the administered dose of inhaled tobramycin.
	• To compare the change in measures of administered respiratory support (FiO ₂ , ventilator mean airway pressure, and respiratory severity score) during the 14-day study period, (1) between participants in the observational cohort and phase 1 trial, and (2) between trial participants stratified by the administered dose of inhaled tobramycin.

	• To evaluate changes (pre vs. post treatment) in airway cytokine levels, neutrophil/WBC ratio, and patterns in the airway microbiome.							
	• To compare changes in the following measures of hypoxemia (SpO ₂ <80%): Intermittent hypoxemia (events lasting 10s-3min), prolong hypoxemia (events lasting >1min), and daily proportion of time in hypoxemia during the 14-day study period, (1) between participants in the observational cohort and phase 1 trial, and (2) between trial participants stratified by the administered dose of inhaled tobramycin.							
	• To evaluate longitudinal change in dynamic lung compliance, airway resistance, peak expiratory flow, and CO ₂ elimination during the 14-day study period, (1) between participants in the observational cohort and phase 1 trial, and (2) between trial participants stratified by the administered dose of inhaled tobramycin.							
Study Drug	Tobramycin solution (300mg/5mL) for inhalation USP							
Study Design	Open-label, inter-patient 3+3 dose escalation trial. An untreated observational cohort of eligible infants will also be enrolled and outcomes compared to trial participants.							
Subject Population	Inclusion Criteria							

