^a "Day 0" procedures to be completed ≤7 days prior to trial Day 1 ^b "Day 15" procedures to be completed ≤48 hours after the final administered dose of inhaled tobramycin (phase 1 trial) or study day 14 (observational cohort)

° Tracheal aspirate sample collected 14 days after the final administered dose of inhaled tobramycin or on the day of planned tracheal extubation, if earlier

^d Serum magnesium and phosphorus levels will be checked with the comprehensive metabolic panel on trial days 7 and 14.

* Up to 6 blood samples (200µL per sample) for pharmacokinetic analyses (PK) will be collected per infant concurrent with clinically ordered blood draws.

page xvi

[figure not shown]

Figure 1. Study enrollment and phases flow diagram.

* Details of both the phase 1 trial and observational (non-treated) cohort will be discussed with eligible families during the consent conversations. Eligible infants may participate in either cohort but can be enrolled in only one cohort.

page xvii

[figure not shown]

Figure 2. 3+3 dose escalation design schematic. MTD: maximum tolerated dose

Up to 4 different dosages of tobramycin solution for inhalation will be investigated using the above 3+3 trial design (78mg, 150mg, 216mg, and 300mg; all administered every 12 hours for up to 14 days). If the 300mg dose level is completed in 3 participants and none show evidence of a toxic response, up to 3 additional infants will be enrolled to receive to receive 300mg. The trial will be stopped if 2 of the additional infants receiving 300mg develop a toxic response and the 216mg dose will be used as the maximum tolerated dose in subsequent trials.

A toxic response is defined as the occurrence of any of the following safety endpoints during the 14-day phase 1 trial (see individual subject and full study stopping rules in section 5.2.4 and 5.2.5 for more details):

- Trough serum tobramycin level (measured 11 hours after the last administered dose) ≥1µg/mL
- Increase in serum creatinine level by ≥0.3mg/dL above the pre-trial level¹⁻³
- Increase in serum creatinine >1.5-fold above the pre-trial level¹⁻³
- Urine output <0.5mL/kg/hr for 12 hours¹⁻³
- Any serious adverse event possibly attributable to the study drug^b

^b The likelihood an adverse event is attributable to a study intervention will be defined as outlined in section 8.3.

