simplified severity score calculated as the MAP multiplied by the FiO₂. The RSS is used in place of the oxygenation index (OI) owing to the infrequent availability of data on the partial pressure of arterial oxygen (PaO₂) in hospitalized infants. The RSS correlates well with OI in infants receiving mechanical ventilation and is a useful predictor of poor respiratory outcomes in preterm infants.⁹²⁻⁹⁴ FiO₂ and MAP values (measured by the mechanical ventilator and reported on the ventilator graphical interface), are recorded at least hourly in the respiratory flow sheet in the electronic medical record (EPIC). These data will be used to calculate daily, time-weighted values for FiO₂, MAP, and RSS. Longitudinal change in these respiratory support measures during the 14-day study period will be compared (1) between infants who participate in the phase 1 trial and those enrolled in the observational (non-treated) cohort, and (2) among participants in the phase 1 trial, stratified by the administered dose of inhaled tobramycin.

Owing to the expected heterogeneity in lung disease and respiratory support requirements of the enrolled infants, a protocolized ventilator management algorithm will not be utilized during this study. However, routine practice in our unit is to wean FiO₂ in infants with BPD to maintain SpO₂ \geq 90%. Most infants with BPD who require invasive respiratory in our unit are supported using a time-cycled, pressure-limited, volume-guarantee mode of ventilation that delivers 8-10mL/kg of tidal volume at mandated rates of 15-25 breaths per minute. The Draeger V500 ventilator is used in all infants receiving acute care in the CHOP N/IICU who are prescribed intermittent mechanical ventilation. On this mode of support, the ventilator automatically adjusts the positive inspiratory pressure (PIP) – within set limits – to deliver the goal tidal volume. Change in the PIP along with any clinical adjustments in the positive end expiratory pressure (PEEP) will be the primary determinants of any observed changes in the delivered MAP. Only infants with an endotracheal tube leak ≤20% will be enrolled in this trial to avoid ventilator leak compensation and artificial inflation of the PIP levels.⁹⁵ Of note, the Draeger V500 ventilator calculates the endotracheal leak proportion during all modes of intermittent ventilation employed in our unit.

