6.4 Sample Size and Power

The traditional 3+3 design is the prevailing method for conducting phase 1 drug trials.^{103,104} The sample size for this design is dictated by the number of different dosages investigated in the trial and whether or not additional patients are added to individual dosage levels based on the occurrence of a toxic drug response. Up to 24 infants are expected to provide analyzable trial data as described in section 3.3.2. The purpose of the 3+3 trial design is to continue dose escalation (within set boundaries) until at least two patients among a cohort of three to six patients experience dose-limiting toxicities (i.e., \geq 33% of patients with a doselimiting toxicity at that dose level).^{103,104} If the 300mg dose level is completed in 3 participants and none show evidence of a toxic response, up to 3 additional infants will be enrolled to receive to receive 300mg. The trial will be stopped if 2 of the additional infants receiving 300mg develop a toxic response and the 216mg dose will be used as the maximum tolerated dose in subsequent trials.

Enrollment in the observational cohort will run concurrent with enrollment in the phase 1 trial. A minimum of 12 infants and a maximum of 28 infants will be enrolled in the observational cohort. This variable enrollment number is selected to avoid delay in study closure if enrollment in the trial cohort out paces the observational cohort. Importantly, these numbers are anticipated to provide adequate statistical power to measure clinically meaningful differences in the frequency of intermittent hypoxemia, an important measure of cardiorespiratory stability.^{96,97} Premature infants with BPD average 75 (SD \pm 9) intermittent hypoxemic events (SpO₂ <80% for 10s-3min) per day during the first several months of life.^{105,106} A sample size of 12 infants in the observational cohort and 12 in the trial cohort will provide >80% power (α =0.05) to detect a 15% difference in the mean daily frequency of intermittent hypoxemic events between the two groups. A sample size of 24 infants per group will provide >80% to detect an 11% difference in in the mean daily frequency of intermittent hypoxemic events.

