in either study cohort will be offered but an infant may only be enrolled in one of the study cohorts (phase 1 trial or observational cohort). Consent for the observational cohort will be obtained either in person or via telephone, through a waiver of documentation of consent.

Before any study procedures take place, all necessary consent forms must be signed by a legally acceptable surrogate and the investigator-designated research professional obtaining the consent.

Consent to participate in the phase 1 drug trial will be obtained by a physician member of the study team. Consent for the phase 1 drug trial will be obtained either through written consent or through electronic consent (also known as eConsent). Electronic consent will utilize the REDCap survey method. The 21 Code of Federal Regulations (CFR) Part 11 compliant version of REDCap will be used to obtain eConsent, and all associated regulations will be followed. If using the REDCap survey, the research team will email the eConsent to the parents. We will follow up with a telephone call or video conferencing to review the details of the trial and allow for all questions to be answered. Parents will then sign the eConsent, which is returned electronically back to the study team. PHI needed for emailing and returning the signed eConsent is only available in the PDF and not in the body of the email or the email subject header, thus maintaining subject confidentiality. REDCap's eConsent automatically returns a signed copy to the parent if he/she agrees to participate.

Parents/guardians with limited English proficiency will consent using the short form process. Short forms in the preferred language will be obtained from the CHOP IRB website. The Study Summary document will be signed by the study team member obtaining consent and the witness/interpreter. The short form document will be signed by the parent/guardian and the witness/interpreter. Consent will only occur in person with the study team, parent/guardian, and interpreter all present.

Whenever feasible, consent conversations will take place in person. At the conclusion of all consent discussions, parent(s) or guardian(s) will be provided the opportunity to ask questions about the study and to discuss the study with their family, friends, and/or other medical professionals. As there are no negative repercussions for lack of participation, we do not anticipate a significant risk of coercion or undue influence to participate.

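### For respiratory support and hypoxemia, treated and untreated infants in non-randomised cohorts are compared by unadjusted tests, and adjustment depends on a linear-looking plot

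*Combined protocol and SAP*

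**What the plan says.** **Who enters which cohort.** Section 9.1 rules out randomisation. The note to Figure 1 says "Eligible infants may participate in either cohort but can be enrolled in only one cohort", and Section 9.6 says that enrolment "in either study cohort will be offered but an infant may only be enrolled in one of the study cohorts", so the family decides. Two other rules shape entry. The attending physician must approve before a family is approached (Section 4.1), and only two infants may be in the drug trial at once (Section 9.5).

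**What is to be compared.** The synopsis objective for hypoxemia is "To compare changes in the following measures of hypoxemia" between the cohorts. Section 5.3 says of FiO2, MAP and RSS: "Longitudinal change in these respiratory support measures during the 14-day study period will be compared". Section 2.2 also asks for change in respiratory support.

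**How it is to be compared.** Section 6.3.3 says: "Non-paired tests will be used to compare data baseline and subsequent data points between the infants in the phase 1 trial" and the observational cohort. No covariates are named. For respiratory support and hypoxemia, Table 7 adds only daily summaries and mixed models that will be considered. For pulmonary mechanics, Table 7 does commit to comparing each infant's change from baseline between cohorts.

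**When adjustment happens.** Confounders enter only in the mixed models, and "these analyses will only be performed on an exploratory basis if graphical evaluations of the study data suggest strong evidence of a linear change". The reporting standard carries the same condition: "If longitudinal models are performed, 95% confidence intervals for all estimates of effect will be reported and caution will be urged".

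**Power.** Section 6.4 claims more than 80% power at 12 per group "to detect a 15% difference in the mean daily frequency of intermittent hypoxemic events between the two groups", and the same at 24 per group for an 11% difference.

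**The concern.** Non-randomised cohorts may differ at entry in severity, age or trajectory. A test of follow-up values cannot separate such a difference from a drug effect. Testing the baseline values as well reveals a gap only if the test happens to detect it, and it adjusts for nothing.

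The trigger for adjustment is also the wrong one. Whether the outcome moves in a straight line over 14 days has no bearing on whether the cohorts started level. A stable gap or a curved response would leave the contrast unadjusted, with no promised interval and no promised caution.

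The quantity is not settled either. The objectives ask for change, while the methods sentence and the power statement are written for values. Two analysts could follow the plan and report different contrasts. Sections 1.7 and 9.4.3 say the data will inform phase 2 and 3 trials, and Section 6.4 presents the hypoxemia contrast as adequately powered, so readers may give it weight.

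**Working it through.** **1. The plan's power figure.** Inputs from Section 6.4: mean 75 events per day, SD 9, alpha 0.05 (taken as two-sided), differences of 15% (0.15 × 75 = 11.25) and 11% (0.11 × 75 = 8.25). A two-sample t-test on raw means gives:

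- 12 v 12: noncentrality (11.25/9) × √(12/2) = 3.06, 22 df, power 83.3%
- 24 v 24: noncentrality (8.25/9) × √(24/2) = 3.18, 46 df, power 87.5%

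The claim of more than 80% reproduces, for an unadjusted comparison of raw means.

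**2. Power for other quantities.** The correlation r between baseline and follow-up is not in the documents; 0.3 to 0.8 is assumed. The SD of change is 9√(2(1−r)); the ANCOVA residual SD is 9√(1−r²).

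| r | Change SD | Change power, 12 v 12 / 24 v 24 | ANCOVA SD | ANCOVA power, 12 v 12 / 24 v 24 |
|---|---|---|---|---|
| 0.3 | 10.65 | 69.6% / 74.8% | 8.59 | 86.6% / 90.3% |
| 0.5 | 9.00 | 83.3% / 87.5% | 7.79 | 92.2% / 94.8% |
| 0.8 | 5.69 | 99.6% / 99.8% | 5.40 | >99% / >99% |

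The ANCOVA formula ignores the lost degree of freedom and chance imbalance. Simulation at r = 0.3 gives 85% and 90%, still above 80%.

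**3. False-positive rate with no drug effect.** Assume one test at two-sided 0.05, equal SDs and a baseline gap of b = 0.5 SD (4.5 events per day for hypoxemia). The gap may be *stable* (follow-up gap b) or *regress* (follow-up gap r × b).

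- Raw test: noncentrality = follow-up gap × √(n/2). Stable gap at 12 v 12: 0.5 × √6 = 1.22, giving 21.6%. Stable gap at 24 v 24: 0.5 × √12 = 1.73, giving 39.6%.
- Change: no bias if stable. If the gap regresses, the bias is (1−r)b with SD √(2(1−r)).
- ANCOVA: no bias if the gap regresses; bias (1−r)b if stable. Rates come from simulation (200,000 trials per cell).

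| 0.5 SD gap | r = 0.3 | 0.5 | 0.7 | 0.8 |
|---|---|---|---|---|
| 12 v 12 raw, stable | 21.6% | 21.6% | 21.6% | 21.6% |
| 12 v 12 raw, regresses | 6.4% | 9.0% | 13.0% | 15.5% |
| 12 v 12 change, regresses | 10.7% | 9.0% | 7.4% | 6.6% |
| 12 v 12 ANCOVA, stable | 13% | 10% | 8% | 7% |
| 24 v 24 raw, stable | 39.6% | 39.6% | 39.6% | 39.6% |
| 24 v 24 raw, regresses | 8.0% | 13.6% | 22.1% | 27.4% |
| 24 v 24 change, regresses | 17.1% | 13.6% | 10.1% | 8.4% |
| 24 v 24 ANCOVA, stable | 22% | 16% | 11% | 8% |

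Change with a stable gap, and ANCOVA with a regressing gap, hold 5% throughout. ANCOVA was below the raw test in every cell. Change was above the raw test at r = 0.3 with a regressing gap.

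At a 0.25 SD gap the raw rates shrink to 5-9% (12 v 12) and 6-14% (24 v 24).

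**4. Would the baseline test warn?** Its power against a true 0.5 SD gap is the same calculation as the stable raw case: 22% at 12 v 12 and 40% at 24 v 24.

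**5. Are the baselines comparable?**

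- Mechanics: Day 0 in treated infants, which the Table 1 footnote allows up to 7 days before Day 1, but Day 1 in untreated infants (Sections 3.3.1, 4.3.3, 5.1.6). Baseline to Day 7 is 7 − 1 = 6 days untreated and at most 6 + 7 = 13 days treated.
- Oximetry: treated infants have 24-48 hours before the first dose (Section 5.1.2). For untreated infants, the synopsis and Section 3.1.3 describe only the 14-day period, while Table 1 marks Day 0.

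**The case against.** The strongest reply is that these endpoints are labelled exploratory throughout, the dose decision does not use them, and the plan limits modelling because the sample is small. That stands, and it limits what is at stake to interpretation. It does not explain why a single baseline covariate should wait on the shape of a plot.

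The methods sentence is loosely worded and follows text about change over time, so change may be intended. That is possible. One sentence would settle it.

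The documents give no imbalance and no correlation, and nothing in them shows that the cohorts differ. They share one unit, the same criteria and concurrent enrolment. This stands: the rates above illustrate exposure, and the 40% figure needs a stable 0.5 SD gap at 24 v 24.

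Three stronger readings are tempting, and the documents do not support them:

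- *Every cohort contrast is unadjusted.* Table 7 already compares change from baseline for pulmonary mechanics.
- *The power claim is wrong.* It reproduces on raw means. Change falls below 80% only towards the low end of the assumed correlations (about 70% and 75% at 0.3).
- *Untreated infants have no baseline.* Table 1 marks Day 0 for their oximetry and respiratory support, so oximetry needs its wording reconciled. The 13-day mechanics interval is a footnote maximum, and no bias can be estimated from it.

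**Conclusion.** The point holds for FiO2, MAP, RSS and hypoxemia. The stated between-cohort method is an unadjusted test at time points, the objectives ask for change, and adjustment, intervals and caution hang on a condition unrelated to confounding.

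Under the stated assumptions (no drug effect, one test, 0.5 SD gap, correlation 0.3 to 0.8), the rejection rates are:

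- raw test: 6-22% at 12 v 12 and 8-40% at 24 v 24
- change: 5-11% and 5-17%
- ANCOVA: about 5% if the gap regresses; 7-13% and 8-22% if it is stable

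Change is the cleaner analysis if the gap is stable, and ANCOVA if it regresses. ANCOVA is the better primary choice because it never did worse than the raw test here and had more power than the raw test or change at each correlation tabulated. Neither removes unmeasured confounding.

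This is an inexpensive improvement to exploratory analyses. It does not touch the 3+3 decision.

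**What to change.** 1. In Section 6.3.3 and Table 7, for each continuous outcome measured in both cohorts, pre-specify one ANCOVA-type estimate adjusted for the infant's own baseline value, with a 95% CI, fitted whatever the plots show. Give change from baseline as the sensitivity analysis.
2. Extend the caution now tied to the mixed models to all cohort contrasts, and label them non-randomised.
3. In Section 6.4, state that the power of more than 80% is for unadjusted raw means. If power is restated for ANCOVA, give the assumed correlation. By the formula it is about 87% to over 99% at 12 v 12 and 90% to over 99% at 24 v 24 for correlations of 0.3 to 0.8, and slightly lower by simulation at the low end.
4. Use the same mechanics baseline window in both cohorts (Table 1 footnote, Sections 3.3.1, 4.3.3 and 5.1.6).
5. Reconcile the synopsis and Section 3.1.3 with Table 1 so that untreated infants clearly have an oximetry baseline.

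Cost: mostly wording. One mechanics session becomes slightly less flexible to schedule. If Table 1's Day 0 mark is not already intended, untreated infants would have 24-48 hours more research oximetry.
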